5.3.2.3. Supplementary Estimators of the Main Estimand of the Key Secondary Endpoint

Supplementary analyses to better interpret the results will be conducted by constructing additional estimators for the main estimand of the key secondary endpoint as defined in Section 5.3.2. This estimator will be based on the ITT set (instead of mITT).

To provide a comprehensive interpretation of the study results and the impact of COVID-19 pandemic on the functional cure at Week 72, the following supplementary estimator will utilize the ITT analysis set.

5.3.2.3.1. Supplementary Estimator 1 (ITT Analysis Set + MI)

For this supplementary estimator, the same estimand defined in Section 5.3.2, statistical model (MCP-Mod, and stratum-adjusted MH test), assumptions and approach to control the Type I error rate, and the same MI rule to handle missing data will be used as for the main estimator (Section 5.3.2.1).

5.3.2.3.1.1. Data Included

All available data from ITT analysis set, after taking into account all the intercurrent events and applying the intercurrent event strategies specified in Section 5.3.2, will be included.

5.3.2.3.2. Supplementary Estimator 2 (ITT Analysis Set + LOCF)

For this supplementary estimator, the same estimand defined in Section 5.3.2, statistical model (MCP-Mod, and stratum-adjusted MH test), assumptions and approach to control the Type I error rate will be used as for the main estimator (Section 5.3.2.1). For Mod-step, model averaging techniques across the statistically significant candidate models obtained from the MCP step will be used to derive the dose-response shape (Mod step).

The missing data approach will follow the LOCF approach as described in Section 5.3.2.2.1.

5.3.2.3.3. Supplementary Estimator 3 (ITT Analysis Set + Tipping Point)

For this supplementary estimator, the same estimand defined in Section 5.3.2, statistical model (MCP-Mod, and stratum-adjusted MH test), assumptions and approach to control the Type I error rate will be used as for the main estimator (Section 5.3.2.1).

This supplementary estimator will use the tipping point approach as described in Section 5.3.2.2.2.

5.3.2.3.4. Supplementary Estimator 4 of the Key Secondary Endpoint (Missing as Non-Response)

For this supplementary estimator, the same estimand defined in Section 5.3.2, statistical model (MCP-Mod, and stratum-adjusted MH test), assumptions and approach to control the Type I error rate will be used as for the main estimator (Section 5.3.2.1).

For Mod-step, model averaging techniques across the statistically significant candidate models obtained from the MCP step will be used to derive the dose-response shape (Mod step).

5.3.2.3.4.1. Assumptions

- Missing Data for ALT, HBV DNA, and HBsAg are missing not at random
- The treatment effect is homogeneous across strata

5.3.2.3.4.2. Missing Data Handling Rule

Participants who withdraw from the study prior to Week 72 will be considered as non-responders. All participants with missing data for the determination of the key secondary endpoint status will be imputed as non-responders.

5.3.3. Supplementary Estimand 1 of the Key Secondary Endpoint (Per-Protocol Analysis Set)

A) Study Intervention:

- Arm 1: JNJ-3989 (100 mg) + JNJ-6379 (250 mg qd) + NA
- Arm 2: JNJ-3989 (200 mg) + Placebo + NA
- Arm 3: JNJ-3989 (100 mg) + Placebo + NA
- Arm 4: JNJ-3989 (40 mg) + Placebo + NA
- Arm 5: Placebo + JNJ-6379 (250 mg qd) + NA
- Historical Control 5%

B) Study Population: HBeAg-positive and -negative chronic HBV-infected patients who are not being treated for their HBV infection (including treatment-naïve participants) or are virologically suppressed by NA treatment and who are able to tolerate the treatment regimen and will comply with the treatment schedule as prescribed.

C) Variable: Response status defined as participants who meet the criteria defining functional cure at Week 72 (responders) as defined in Section [5.3.1](#).

D) Intercurrent events:

- Treatment discontinuation prior to Week 48: if the participant discontinued treatment prior to Week 48 then s/he will be considered non-responder (composite strategy).
- Deaths prior to Week 72 are handled in a composite strategy as participants who die prior to Week 72 will be considered as non-responders.
- NA re-treatment between Week 48 and 72: the participant will be counted as non-responder (composite strategy).

E) Population-level summary: Difference in proportion of participants with functional cure status at Week 72 between study intervention arms.

5.3.3.1. Main Estimator

5.3.3.1.1. Analysis Methods

Statistical Model

Similar MCP-Mod and stratum-adjusted MH test on the difference of proportions as described for the main estimator of the main estimand will be used (see Section [5.3.2.1](#)).

5.3.3.1.2. Data Included

All available data from randomized participants that are included in the PP2 analysis set will be used, after taking into account the intercurrent events and applying the intercurrent event strategies specified in Section [5.3.3](#).

To complement this analysis because of its inherent bias and allow a better interpretation of the results, the proportions of participants excluded from the PP2 analysis set will be summarized by intervention arm and by type of major protocol deviation.

5.3.3.1.3. Assumptions

- The treatment effect is homogeneous across strata

5.3.3.1.4. Missing Data Handling Rule

Participants who withdraw from the study prior to Week 72 will be considered non-responders. For the participants still in the study at Week 72 or for participants that have neither discontinued treatment early nor experienced any major protocol violations as listed in [ATTACHMENT 1](#) (PP1 column), but HBsAg values missing at Week 72, then the primary method to handle missing data will be the imputation to non-responder.

5.3.4. Supplementary Estimand 2 of Key Secondary Efficacy Endpoint (vs NA Control Arm)

A) Study Intervention:

- Arm 1: JNJ-3989 (100 mg) + JNJ-6379 (250 mg qd) + NA
- Arm 2: JNJ-3989 (200 mg) + Placebo + NA
- Arm 3: JNJ-3989 (100 mg) + Placebo + NA
- Arm 4: JNJ-3989 (40 mg) + Placebo + NA
- Arm 5: Placebo + JNJ-6379 (250 mg qd) + NA
- Arm 6: Placebo + Placebo + NA

B) Study Population: HBeAg-positive and -negative chronic HBV-infected patients who are not being treated for their HBV infection (including treatment-naïve patients) or are virologically suppressed by being treated with NA.

C) Variable: Response status defined as participants who meet the criteria defining functional cure at Week 72 (responders) as in Section [5.3.1](#).

D) Intercurrent events:

- Treatment discontinuation prior to Week 48: if the participant discontinued treatment prior to Week 48 then s/he will be considered non-responder (composite strategy).
- Major protocol deviations affecting efficacy: [ATTACHMENT 1](#) identifies the deviations considered intercurrent event (in per protocol set 2 column [PP2]). Participants with such deviations and who have missing data for the endpoint will be considered as non-responders (composite strategy). For all other deviations not considered intercurrent events, the data are used regardless of the occurrence of major protocol deviations (treatment policy strategy).
- Deaths prior to Week 72 are handled in a composite strategy as participants who die prior to Week 72 will be considered as non-responders.
- NA re-treatment between Week 48 and 72: the participant will be counted as non-responder (composite strategy).

E) Population-level summary: Difference in proportion of subjects with functional cure status at Week 72 between study intervention arms.

5.3.4.1. Main Estimator

To assess the functional cure rate against the observed proportion in the control Arm 6, for this estimator, the same statistical model (MCP-Mod, and stratum-adjusted MH test), data included, assumptions, and MI approach for handling missing data and approach to control the Type I error rate will be used as for the main estimator of the main estimand for the primary endpoint (Section [5.2.2.1](#)). The MCP-Mod approach and pairwise statistical tests to compare with control will be based on the data from Arm 6 instead of historical control fixed value of 5%. The MCP-step will use the actual data from Arm 6, and statistical test to compare Arm 1 and Arm 5 to control will be the MH test as it compares 2-sample proportions.

5.3.4.1.1. Data Included

All available data from mITT analysis set, is included after taking into account all the intercurrent events and applying the intercurrent event strategies specified in Section 5.3.4.

An additional analysis of this estimand will be performed using the ITT analysis set, after taking into account all the intercurrent events and applying the intercurrent event strategies specified in the previous Section 5.3.4, will be included.

5.3.4.1.2. Assumptions

- Missing Data for HBsAg are Missing At Random (MAR)
- The treatment effect is homogeneous across randomization stratification strata

5.3.4.1.3. Missing Data Handling Rule

Participants who withdraw from the study prior to Week 72 will be considered as non-responders. For other missing data, the same datasets resulting from the MI approach as described in Section 5.3.2.1.4 will be used.

5.3.5. Other Analyses of The Key Secondary Endpoint

The following secondary analyses will be performed for the functional cure rate 24 weeks off treatment.

1. A participant will be defined as having achieved functional cure if he/she has:

- completed 48 weeks of treatment, and
- met the criteria for stopping NA treatment at Week 48, and
- had HBsAg seroclearance between Week 60-72, inclusive, in case of early withdrawal, and
- not required NA re-treatment in the 12-24 weeks after stopping all study intervention.

If the HBsAg value at Week 72 is missing (including the case of early withdraw from the study prior to Week 72), the last/earliest available lab test no earlier/later than 12 weeks prior/after Week 72 will be used in the imputation (Week 60 and 84, respectively).

2. Participants with HBsAg seroclearance 24 weeks after stopping all study interventions (regardless of the actual duration of treatment and regardless of meeting the criteria for stopping NA treatment) without restarting NA treatment will be considered as having achieved FC. A participant will be defined as having achieved functional cure if he/she has:

- stopped all study treatment at some point in time, and
- had HBsAg seroclearance 24 weeks after stopping all study interventions, and
- not required NA re-treatment in the 24 weeks after stopping all study intervention.

If the HBsAg value 24 weeks after treatment completion is missing, the LOCF in conjunction with the next available observation imputation approach will be used with a 12-week window prior/after the timepoint of 24 weeks post stopping all treatments.

The following analyses of functional cure rate will be based on different analysis sets, i.e., a subset of mITT, ITT and PP2 analysis set.

3. Functional cure rate at Week 72 will be calculated for the subset of those participants in the selected analysis set who are responders for the primary efficacy endpoint (i.e. the denominator is the count of participants meeting the NA treatment completion criteria at Week 48, Section 5.2.1).

If the HBsAg value at Week 72 is missing (including the case of early withdraw from the study prior to Week 72), the last/earliest available lab test no earlier/later than 12 weeks prior/after Week 72 will be used in the imputation (Week 60 and 84, respectively).

Descriptive summary and 90% CIs will be performed for the secondary analyses. The differences in functional cure rate between intervention arms will be summarized using Mantel-Haenszel method adjusted for the 2 randomization stratification factors. No adjustment for multiplicity will be made in these secondary analyses.

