5.2. Primary Efficacy Endpoint

5.2.1. Definition

The primary efficacy endpoint is defined as the proportion of participants meeting the NA treatment completion criteria **at Week 48**.

A participant will be defined as responder in meeting the NA treatment completion criteria at Week 48, if the following criteria are met based on the clinical laboratory tests performed **at Week 44**:

- ALT <3x upper limit of normal (ULN), AND
- HBV DNA <LLOQ, AND
- HBeAg-negative (<LLOQ), AND
- HBsAg <10 IU/mL.

Note: In case of ALT elevation $\geq 3x$ ULN at Week 44, the ALT re-test before Week 48 may be performed. If the ALT re-test meets the criteria above, the participant will be considered as responder as satisfying the NA treatment completion criteria.

Note: Quantitative HBeAg assessment is only performed at Week 44 for participants who are HBeAg positive at screening. Therefore, if a participant is HBeAg negative at screening, they are assumed to be negative at Week 44 for the purpose of the primary endpoint.

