5.3. Key Secondary Endpoint

5.3.1. Definition

The key secondary endpoint is the proportion of participants having HBsAg seroclearance 24 weeks after stopping all study interventions at Week 48. This endpoint will be called as “functional cure” at week 72 interchangeably in the rest of this document.

A participant will be defined as having achieved functional cure (FC) at Week 72 if he/she has:

- met the criteria for stopping NA treatment at Week 48, and
- had HBsAg seroclearance at Week 72 (i.e. 24 weeks after stopping all study interventions), and
- not required NA re-treatment between Weeks 48 and 72.

Seroclearance of HBsAg is defined as HBsAg level<LLOQ. It can be noted that a participant may achieve HBsAg seroclearance prior to Week 72, but the HBsAg level<LLOQ has to be shown at Week 72 to be counted as responder.

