5.3.2.1.2. Data Included

All available data from mITT analysis set, is included after taking into account all the intercurrent events and applying the intercurrent event strategies specified in Section 5.3.2.

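### The between-arm functional cure difference among primary-endpoint responders only (SAP 5.3.5, item 3) is not a randomised comparison and can be null or opposite in sign to the full-set difference

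*SAP*

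**What the plan says.** Item 3 of SAP 5.3.5 calculates functional cure "for the subset of those participants in the selected analysis set who are responders for the primary efficacy endpoint", and adds that "the denominator is the count of participants meeting the NA treatment completion criteria at Week 48". It is to be run on subsets of mITT, ITT and PP2. The closing paragraph of 5.3.5 asks for descriptive summaries with 90% intervals and continues: "The differences in functional cure rate between intervention arms will be summarized using Mantel-Haenszel method adjusted for the 2 randomization stratification factors". It also states: "No adjustment for multiplicity will be made in these secondary analyses". Nothing there separates item 3 from items 1 and 2.

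Responder status comes from SAP 5.2.1, where a participant responds "if the following criteria are met based on the clinical laboratory tests performed" at Week 44, that is, on treatment. Functional cure as defined in SAP 5.3.1 already includes response as a condition: the participant must have "met the criteria for stopping NA treatment at Week 48, and" then have HBsAg seroclearance at Week 72 without NA re-treatment.

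The main key secondary estimator is not restricted to responders. SAP 5.3.2.1.2 reads: "All available data from mITT analysis set, is included after taking into account all the intercurrent events".

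**The concern.** Randomisation makes whole arms comparable. It does not make comparable the parts of those arms that reached an on-treatment threshold, when the treatments differ in how many participants they bring to it. An arm with more responders includes people who would not have responded on the other arm, and their chance of lasting HBsAg loss may differ from that of people who respond on either. The adjustment uses only screening HBeAg status and treatment history, so it cannot remove this difference.

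Functional cure requires response, so its rate in an arm is the response rate multiplied by the cure rate among responders. Item 3 keeps only the second factor and so removes the treatment effect on response. A stratified difference with a confidence interval nevertheless reads as a treatment effect. The SAP notes inherent bias for its per-protocol analyses (5.2.4.1.2 and 5.3.3.1.2) but gives no such caution for item 3. At stake is how a reader interprets regimen and dose differences from this output.

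**Working it through.** **Inputs from the documents.** 90 participants in each of Arms 1 to 4 and 45 in each of Arms 5 and 6. Planning response rates are 50% in Arm 1, 25% in Arms 3 and 5 and 5% in Arm 6 (SAP 1.4; protocol 9.2, Table 7). No cure rate among responders is given for any arm.

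**Reproducing the planning figure.** At 50%, 25% and 25%, one-sided 0.05 with a pooled normal test, calculated power is 0.970 for Arm 1 vs Arm 3 and 0.889 for Arm 1 vs Arm 5. A 400,000-run simulation gives 0.871 for the min test. Table 7 gives 0.970, 0.889 and 0.871. The response rates used below are therefore the plan's own.

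**Expected responders (the item 3 denominators).**
- Arm 1: 0.50 × 90 = 45
- Arm 3: 0.25 × 90 = 22.5
- Arm 5: 0.25 × 45 = 11.25
- Arm 6: 0.05 × 45 = 2.25

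Arm 1 vs Arm 3 would thus set half of one arm against a quarter of the other.

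**Full-set and responder-only differences.** Assume that everyone who would respond on Arm 3 (25%) would also respond on Arm 1, with the same cure rate a on either arm. Assume a further 25% respond only on Arm 1, with cure rate b.
- Full set: (0.25a + 0.25b) - 0.25a = 0.25b
- Responders only: (0.25a + 0.25b)/0.50 - a = 0.5(b - a)

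Under this model the full-set difference is never negative, and the responder-only difference is negative whenever b is below a. With a = 40% (assumed):

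| b | Full set, Arm 1 vs Arm 3 | Difference | Responders, Arm 1 vs Arm 3 | Difference |
|---|---|---|---|---|
| 40% | 20% vs 10% | +10 | 40% vs 40% | 0 |
| 20% | 15% vs 10% | +5 | 30% vs 40% | -10 |
| 10% | 12.5% vs 10% | +2.5 | 25% vs 40% | -15 |
| 0% | 10% vs 10% | 0 | 20% vs 40% | -20 |

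**Effect of stratification.** Protocol 4.1 aims for 40% not currently treated, of whom 40% are expected to be HBeAg-positive, which gives strata of 16% and 24%. The remaining 60% was split 30% and 30% by assumption. With the same rates in every stratum and a = 40%, b = 10%, the Mantel-Haenszel difference is -15 points among responders and +2.5 points in the full set, unchanged by the adjustment.

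**In a single trial, a = 40%, b = 10% (400,000 runs, unstratified).** The responder-only estimate favours Arm 3 in 89% of trials. It does so while the full-set estimate favours Arm 1 in 55%. Its 90% interval excludes zero in favour of Arm 3 in 34%. At b = 20% these figures are 78%, 60% and 20%. At b = 40% the interval excludes zero in that direction in 5%, about the nominal one-sided rate.

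**Sparsity.** The chance of no responders in Arm 6 is 0.95^45 = 0.099, about 10%. A stratum contributes to the Mantel-Haenszel difference with weight n1 × n0/(n1 + n0), which is zero when either arm has no responder there. With 2.25 expected responders over four strata, several strata will often drop out of any contrast with Arm 6.

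**The case against.** Item 3 sits among supportive analyses, with no hypothesis, alpha or decision rule. A reader might infer that it could lead the formal dose or regimen choice astray. The documents do not support that: protocol 9.4.1.2 gives the selection role to functional cure under the multi-step testing strategy, and SAP 5.3.2.1 runs those tests on mITT. The unrestricted functional cure results and the response rates will also be reported, so a careful reader could see both factors. This stands, and it limits the point to interpretation.

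It is also fair that every responder meets the same HBsAg cut-off, and that nothing in the documents shows a more active arm to have weaker additional responders. A reader might infer that the difference will favour the worse regimen. It need not: at equal cure rates it is zero, and if the extra responders did better it would be positive.

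A third tempting reading is that the responder groups are nearly empty throughout. That applies mainly to Arm 6. Arm 5 would have about 4.5 responders (0.10 × 45) only in the 4 of 13 Table 7 rows that assume 10%; the other nine assume 25% to 35%, or about 11 to 16. Arm 6 is also not the comparator in the main functional cure test, which uses the 5% historical value.

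None of this makes the responder-only contrast a randomised one. Showing the full-set result beside it, with a caution, would help the reader but would still leave a difference and interval that do not estimate a treatment effect.

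**Conclusion.** The point holds as a matter of interpretation. Followed as written, SAP 5.3.5 produces a between-arm difference in a group selected by an outcome that treatment is planned to change. At the plan's own 50% and 25% response rates, a full-set advantage of 10 points for Arm 1 becomes 0 among responders if all are cured at 40%. An advantage of 2.5 points becomes -15 if the extra responders are cured at 10%. These sizes rest on assumed cure rates, on no one responding to Arm 3 alone, and on common responders doing equally well on either arm; other values move both figures. What does not depend on them is that the contrast lacks the protection of randomisation. The Arm 6 contrasts are doubtful for the separate reason of very small numbers. The formal key secondary tests are untouched, and each arm's rate among responders remains a legitimate description of how durable the response is after NA is stopped.

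**What to change.** Add one sentence to the closing paragraph of SAP 5.3.5: for item 3, only each arm's functional cure rate with a 90% confidence interval is reported, using the exact Clopper-Pearson method because counts may be small, and no between-arm difference is calculated. Keep the Mantel-Haenszel differences for items 1 and 2 and for the main analyses on their full mITT or ITT denominators. The restriction should not be worded as all randomised and treated participants, since that would exclude mITT, the SAP's primary efficacy set.

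The cost is one sentence and fewer outputs. No data collection, main test or alpha allocation changes, and the by-arm durability rate is kept.

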5.3.6. Subgroup Analyses of The Key Secondary Endpoint

The potential association between the functional cure rate and the randomization stratification factors will be explored by a multivariate logistic regression model and exploration of the interaction terms using observed case data. The model will include intervention arm, treatment history and HBeAg status at screening, as factors, and the intervention arm-by-treatment history and intervention arm-by-HBeAg status interaction terms. The functional cure estimates for each intervention arm will be derived from this model and presented graphically with their 90% CI in a forest plot. In addition, for assessment of internal consistency and investigation of homogeneity of the treatment effect in functional cure across other subgroups (as defined in Section 2.4.1), the same logistic regression approach as defined in Section 5.2.5 will be used.

5.4. Other Secondary Endpoints

Statistical comparisons of all other secondary endpoints among intervention arms will be done with no adjustment for multiplicity.

In addition, the potential association between treatment outcome and baseline factors will be explored by multivariate logistic regression model in a similar fashion as described in Section 5.2.5.

5.4.1. HBsAg Seroconversion

HBsAg seroclearance will be evaluated over all time points when assessed, with emphasis at the following time points:

- at Week 48
- at Week 96 (ie, 48 weeks after completion of all study interventions at Week 48) without restarting NA treatment,

- 12 weeks after stopping all study interventions (regardless when intervention was stopped) without restarting NA treatment, and
- 24 weeks after stopping all study interventions (regardless when intervention was stopped) without restarting NA treatment, and
- 36 weeks after stopping all study interventions (regardless when intervention was stopped) without restarting NA treatment, and
- 48 weeks after stopping all study interventions (regardless when intervention was stopped) without restarting NA treatment

Proportions at the time points listed in the above bullets will be analyzed using the Mantel-Haenszel test and 90% CIs stratified for treatment history status and screening HBeAg status.

5.4.1.1. At Week 48 and At Week 96

The proportion of participants achieving HBsAg seroclearance at EOT (Week 48), and at Week 96 (48 weeks after completion of all study interventions at Week 48) will be summarized by intervention arm. A participant will be defined as responder at Week 96 (with HBsAg seroclearance 48 weeks after completion of all study intervention at Week 48) if he/she has completed 48 weeks of treatment AND met the criteria for stopping NA treatment at Week 48 AND not required NA re-treatment between Week 48 and Week 96 AND had HBsAg seroclearance at Week 96. If the HBsAg value at Week 96 is missing, the LOCF approach will be used with the condition that no value earlier than Week 84 may be carried forward.

Those participants who did not meet the NA stopping criteria at Week 48 OR did not complete 48 weeks of treatment OR did not reach seroclearance at Week 96 will be defined as non-responders for Week 96. The participants who has no HBsAg value between Week 84 and 96 or required NA re-treatment prior to Week 96 will be considered as non-responder as well.

If the HBsAg value at Week 48 is missing, the LOCF approach will be used with the condition that no value earlier than Week 40 may be carried forward. Those participants who did not meet the NA stopping criteria at Week 48 OR did not complete 48 weeks of treatment OR did not reach seroclearance at Week 48 will be defined as non-responders for Week 48. The participants who has no HBsAg value between Week 40 and 48 or will be considered as non-responder as well.

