ICS intracellular cytokine staining

IDMC Independent Data Monitoring Committee

IEC Independent Ethics Committee
IFLEP Independent Flare Expert Panel

 $\begin{array}{ll} \text{IFN} & \text{interferon} \\ \text{IFN-}\gamma & \text{gamma interferon} \\ \text{IgM} & \text{immunoglobulin M} \end{array}$

IL interleukin

INR International Normalized Ratio
IRB Institutional Review Board
ISR injection site reaction

ITT Intent-to-treat

IU/mL International Units Per Milliliter IWRS interactive web response system

LLN lower limit of normal LLOQ lower limit of quantification

MCP-Mod Multiple Comparison Procedure-Modeling

MCT Multiple Contrast Test
MH Mantel-Haenszel
MoA mode of action

MRI magnetic resonance imaging

NA nucleos(t)ide analog

NOAEL no observed adverse effect level

PD pharmacodynamic(s)

PGIC Patient Global Impression of Change

PK pharmacokinetic(s)

PBMC peripheral blood mononuclear cell pgRNA pre-genomic ribonucleic acid

PI prediction interval

PQC Product Quality Complaint PRO patient-reported outcome

qd once daily

QTcF QT interval corrected for heart rate according to Fridericia

RBC red blood cell RNA ribonucleic acid

 $\begin{array}{lll} RNAi & ribonucleic \ acid \ interference \\ SAE & serious \ adverse \ event \\ SAP & Statistical \ Analysis \ Plan \\ SBP & systolic \ blood \ pressure \\ SD & standard \ deviation \\ SigE_{max} & sigmoid \ E_{max} \end{array}$

siRNA small interfering RNA

SUSAR suspected unexpected serious adverse reaction

 $t_{1/2 term}$ terminal half-life

t_{max} time to reach the maximum plasma concentration TAF tenofovir alafenamide

TDF tenofovir disoproxil fumarate TNF tumor necrosis factor

ULN upper limit of normal US United States WBC white blood cell

Definitions of Terms

Study intervention JNJ-73763989 or placebo, JNJ-56136379 or placebo, and NA (either ETV, TDF, or TAF)

Functional cure HBsAg seroclearance 24 weeks after end of treatment

HBsAg or HBeAg

seroclearance

HBsAg or HBeAg negativity, respectively, based on the assay used

HBsAg or HBeAg seroconversion

HBsAg or HBeAg negativity and anti-HBs or anti-HBe antibody positivity, respectively

Virologic

breakthrough

Confirmed on-treatment HBV DNA increase by >1 log₁₀ IU/mL from nadir or confirmed on-treatment HBV DNA level >200 IU/mL in participants who had HBV DNA level

<LLOQ of the HBV DNA assay

ALT/AST nadir Lowest ALT/AST value during study participation

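### SAP 5.4.1.1 labels an outcome HBsAg seroclearance at Week 48 but scores participants with HBsAg below LLOQ as non-responders if they missed the NA stopping criteria or did not complete 48 weeks

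*SAP*

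**What the plan says.** SAP Section 5.4.1.1 introduces the outcome as "The proportion of participants achieving HBsAg seroclearance at EOT (Week 48), and at Week 96". The Week 48 paragraph first allows a missing HBsAg value to be carried forward from no earlier than Week 40. It then gives the scoring rule, which begins "Those participants who did not meet the NA stopping criteria at Week 48 OR did not complete 48 weeks of treatment" and ends, after a further OR, with those who "did not reach seroclearance at Week 48 will be defined as non-responders for Week 48". Any one of the three is enough for non-response.

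SAP Section 5.3.1 states: "Seroclearance of HBsAg is defined as HBsAg level<LLOQ". Section 5.4.11.1 uses the same definition for time to seroclearance. Protocol Appendix 1 defines it as "HBsAg or HBeAg negativity, respectively, based on the assay used". None of these refers to the NA criteria.

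The NA stopping criteria are in SAP Section 5.2.1 and use Week 44 laboratory tests. They include "ALT <3x upper limit of normal (ULN), AND" and "HBV DNA <LLOQ, AND", together with a negative HBeAg and HBsAg under 10 IU/mL. Two notes soften them. An ALT re-test before Week 48 that meets the limit counts as meeting the criterion. Participants who were HBeAg-negative at screening are assumed negative at Week 44.

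**The concern.** The label and the rule describe different outcomes. A reader of a table headed HBsAg seroclearance at Week 48 will take the proportion to be those with HBsAg below LLOQ. Under the rule it is the proportion with HBsAg below LLOQ who also completed 48 weeks and met three requirements on other markers four weeks earlier. Missing-data handling aside, a Week 48 responder must already be a responder on the primary endpoint, so the figure cannot show clearance outside that group.

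Section 5.4.1 assigns this proportion a stratified Mantel-Haenszel test and a 90% CI, so the mismatch affects a between-arm comparison as well as a descriptive count. It also allows inconsistent reporting. HBsAg seroconversion in Section 5.4.9 needs HBsAg below LLOQ plus appearance of anti-HBs, with no NA condition. The same participant could be seroconverted at Week 48 and not cleared at Week 48.

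**Working it through.** No sample size, power or alpha figure in the documents depends on this outcome, so there is no planned figure to reproduce. The check is logical.

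**Inputs.**
- Cleared at Week 48: HBsAg below LLOQ, which is 0.05 IU/mL (SAP Table 3).
- NA criteria at Week 44: ALT below 3x ULN after any re-test, HBV DNA below LLOQ (20 IU/mL, SAP Table 3), HBeAg negative, HBsAg below 10 IU/mL (SAP 5.2.1).
- Completed 48 weeks: yes or no.

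**Rule as written.** Responder = (all four NA criteria met) AND (48 weeks completed) AND (HBsAg below LLOQ at Week 48).

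**Enumeration.** Hold Week 48 HBsAg below LLOQ and let each of the other five conditions be met or not met.
- All profiles: 2^5 = 32. One is a responder; 31 are non-responders.
- Treatment completed: 2^4 = 16. One is a responder; 15 are non-responders.
- Screening HBeAg-negative, where the HBeAg condition is always met: 2^4 = 16. One is a responder; 15 are non-responders.

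These are counts of logical profiles, not patient frequencies. They show that the rule depends on conditions other than HBsAg clearance. Three single-failure profiles, each with treatment completed and HBsAg cleared, are scored as failures:
- HBV DNA at or above LLOQ at Week 44.
- HBeAg positive at Week 44 (screening-positives only).
- ALT at or above 3x ULN at Week 44, not resolved on re-test.

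Under a rule of HBsAg below LLOQ alone, all 32 profiles count as cleared.

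**Direction.** The rule adds conditions joined by AND. With the same denominator and the same carry-forward window, the reported proportion is at most the HBsAg-below-LLOQ proportion. They are equal when no cleared participant fails another condition.

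**Size per participant.** 1/90 = 1.1 percentage points (Arms 1 to 4 as planned); 1/45 = 2.2 percentage points (Arms 5 and 6).

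**Illustration (assumed values).** If a proportion p of an arm is cleared and a fraction f of those fail another condition, the reported rate is p(1 - f). With p = 10% in an arm of 90 (9 participants):
- f = 10%: 10% x 0.9 = 9%.
- f = 20%: 10% x 0.8 = 8%.
- f = 40%: 10% x 0.6 = 6%.

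The documents give neither p nor f.

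**The case against.** The best defence is that the composite is deliberate. Study intervention includes NA, and under Protocol Section 6.6 participants who miss the criteria continue NA in follow-up. Only those meeting the criteria stop everything at Week 48, so requiring them would parallel the Week 96 outcome and functional cure. It would therefore be wrong to argue that everyone is off all treatment at Week 48. The defence still does not reconcile label and rule. SAP Table 2 defines EOT as the last post-baseline double-blind visit. In the Section 5.4.1 list, Week 48 alone carries no condition about restarting NA. Section 5.4.1.2 expressly sets aside the NA criteria and treatment duration.

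The defence is stronger on completion of 48 weeks. The main estimands also score some or all early discontinuers as non-responders, so that is a legitimate estimand choice if stated.

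A second defence is that the unconditioned result is already planned. Section 5.4.5.2 tabulates HBsAg below 0.05 IU/mL by arm over time, and Section 5.4.11.1 analyses time to first HBsAg below LLOQ. This limits the damage, but neither analysis corrects the Week 48 Mantel-Haenszel comparison.

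A reader might also infer four stronger points that the documents do not support:
- That the Week 96 rule was copied to Week 48 by mistake. The parallel wording makes this plausible, but it is inference, and the amendment log is not evidence of an error.
- That the shortfall falls mainly on HBeAg-positive or untreated participants. The HBeAg condition can affect only screening-positives, but no rate of NA-criteria failure among cleared participants is given.
- That one misclassified participant would be a large share of events. That needs an assumed number of clearances per arm.
- That the Week 48 figure will certainly disagree with the other tables. On this account it differs only if a cleared participant fails another condition.

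**Conclusion.** The point holds as a conflict between the named outcome and its scoring rule. The stated rule can report a participant with HBsAg below LLOQ as not cleared, in the Week 48 comparison and its 90% CI. The direction is certain given a common denominator and carry-forward window: equal or lower, never higher. The size is unknown beyond the 1.1 or 2.2 points per affected participant at planned arm sizes. Whether the difference between arms is distorted, and which way, cannot be determined.

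The stakes are moderate. The outcome is a non-key secondary one, has no multiplicity adjustment, and is outside the primary and key secondary testing strategy. The conclusion rests on the text of the SAP, not on any assumption about the sponsor's intent.

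**What to change.** In SAP Section 5.4.1.1:
- Define the Week 48 responder as HBsAg below LLOQ at Week 48, with carry-forward from no earlier than Week 40, irrespective of the NA stopping criteria.
- State explicitly whether not completing 48 weeks counts as non-response.
- Repair the last sentence of the Week 48 paragraph, on participants with no HBsAg value between Weeks 40 and 48. It breaks off after a conjunction with the second condition missing.
- Keep the NA-criteria condition for Week 96, where the outcome is seroclearance after all study intervention stopped at Week 48.
- If the Week 48 composite is wanted, report it separately under a name that says what it requires.

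The cost is an edit to one SAP paragraph and the matching derivation. No new data are needed, and no sample size or alpha allocation changes.
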